## consent

- Describe the steps that will be taken by the research team to minimize the possibility of coercion or undue influence during the consent process

For Aim 1, participants will include approximately 250 adults who are current smokers from the Greater St. Louis Area. The research team will recruit subjects from the existing COGA study (IRB ID 201105402) and GISC study (IRB ID 201305128), including only those who are current smokers, and will also Epic/MyChart and work with Volunteer for Health (VFH) to identify and enroll individuals who are current smokers and at least 18 years of age. Participants can search for and volunteer to be enrolled in this study or may be identified as potentially eligible for this study. Through word-of-mouth, participants may also provide us with contact information for others who may be interested in participating. Once identified, the principal investigator will send the postal mail recruitment letter or email recruitment letter to potential participants who can then contact the research team to find out more about the study and set up an in-person or electronic consent (e-Consent) and screening visit or phone call, as desired. Informed consent will be obtained from all subjects by a trained research assistant. E-Consent will be conducted in REDCap, and we will email to the participant a link to the e-Consent to complete. Participants will be able to download or print a copy of the consent from REDCap. Participants will have the option to receive a signed copy of their consent emailed to them by the research team via REDCap. During the in-person consent visit or e-Consent, participants will be provided with a copy of the consent form for review and given the opportunity to ask questions prior to agreeing to participate. Participants will be assured that they can choose not to participate or can discontinue participation at any time without losing any benefits for which they would otherwise qualify. Participants for this study will also be invited to consent to be enrolled in the ICTS Genomic Database Protocol (IRB# 201902019). This protocol allows their genetic data, research data and electronic health care data to be placed in the ICTS Genomic Database for future research. Details for the ICTS Genomic Database Protocol are provided in the ICTS Genomic Database IRB.

For the brief V5 follow-up, we will reach out to participants by email, mail, and phone to re-engage participants in completing the phone call visit. Participants will be consented by phone using the Genimp phone consent (attached for review). A member of the research team will review the consent with the participant, answer any questions they have, and ask for their verbal consent to participate in the visit.

As a developmental activity prior to the above research study, two research team members will use a brief script to engage with a convenience sample of individuals walking through various areas of campus, as well as in brief interactions with staff members (e.g., substance abuse counselors) who work at the National Council on Alcoholism and Drug Abuse – St. Louis Area (NCADA). Interactions with NCADA staff may instead take place in meeting rooms at NCADA or at Washington University. We will request that individuals spend 30-60 seconds giving feedback on the design and formatting of a sample template of the personalized genomic results profile, or report card (see attachments). The goal is to maximize clarity, simplicity, appeal, and usefulness of the report card for future participants. We will conduct this activity by setting up a table for people to walk up to, as well as a more mobile, free-range approach of walking around to solicit feedback from other individuals on campus. Participants of this brief activity may include healthcare professionals, academicians, students, patients, or other members of the public. This activity will take place intermittently at various times for up to 6 hours per week for up to 3 weeks, until saturation of design-related themes is reached. The brief script will be used to request participation, and if individuals decline or do not show interest in participating, they will simply be thanked for their consideration.

Participants will include a group of current smokers (n=20) and a group of clinicians and peer support specialists (n=10) in a partnering community health agency (Wellbridge Addiction Treatment and Research). The current smokers will be adults who are inpatient at Wellbridge for substance abuse treatment and the clinicians will be substance abuse counselors who work at Wellbridge. The peer support specialists will include former Wellbridge clients who have successfully maintained their sobriety and now assist with treatment of new patients. A member of the research team will recruit participants for the study by posting flyers (attached for review) at Wellbridge Treatment Center. One poster will be targeted for recruitment of patients who are current smokers and the other will be targeted for clinicians. Individuals interested in participating will be instructed to contact the research team to sign up. The research team member will make it clear that participation in the study is completely optional and is not a requirement of the treatment program and that they can stop their participation at any time. For potential participants who are patients, a member of the research team will verify that they are a current smoker at this time. For potential participants who are patients, a member of the research team will ask them a couple screening questions to verify that they are a current tobacco smoker at this time. Potential participants will be given as much time as they need to decide about participation. Individuals who are interested in participating will then be scheduled for a focus group by a member of the research team.

Prior to the focus group, a member of the research team will provide participants with an information sheet (attached) that describes the main points of the study and what participation involves. Participants will then have the opportunity to ask the research team member any questions they have prior to participating.

For the Aim 2 small scale feasibility trial, current smokers (N=25) and counselors or peer support specialists (n=10) will be recruited and enrolled from the Wellbridge Treatment Center using the procedures described above. Individuals who are interested in participating will be asked to contact a member for the research team. Prior to participation in the small scale feasibility trial, a research team will obtain consent from current smokers at Wellbridge Treatment center using a paper copy of the consent. During the consent process, current smokers will be provided with a copy of the consent form for review and given the opportunity to ask questions prior to agreeing to participate. Current smokers will be assured that they can choose not to participate or can discontinue participation at any time without losing any benefits for which they would otherwise qualify and that their participation in the study is completely voluntary. A signed copy of the consent will be provided to current smokers. Counselors and peer support specialists will be provided with a copy of the clinician consent form to review and given the opportunity to ask questions before being asked to sign.

- 1.13** Provide a detailed description in sequential order of the study procedures following the consent process - DO NOT cut and paste from the Consent Document.

Describe study populations separately if they will be participating in different procedures

DESCRIBE:

- Control populations, if applicable
- Any randomization, if applicable
- What participants will be asked to do/what happens in the study (in sequential order)
- The time period over which procedures will occur
- Long-term follow-up and how it occurs

For Aim 1, via in-person or remote (phone or Zoom) interviews, we will ask baseline questions about smoking behaviors and genetic knowledge and then offer genetic testing to the participant. As an objective measure of acceptability, we will track the proportion of eligible participants who decline the genetic testing; this will inform how many individuals must be targeted to achieve desired samples in future research. This interview will take approximately 20 minutes. During the in-person visit, participants will contribute DNA via saliva sample; during remote visits, participants will contribute DNA via saliva sample using a 23andMe kit that was mailed to them. We will give each participant a tube to collect each saliva sample. Participants will spit into the tube until there is enough saliva in the tube. This typically takes 1 to 5 minutes. The research team (for in-person visits) or the participant (for remote visits) will send the saliva samples to 23andMe for genetic testing and analysis in a CLIA certified laboratory. Saliva samples sent to 23andMe will be registered via an on-line account created by the participant on the 23andMe website using their personal email address. Participants must provide first and last name, sex and date of birth to register their saliva sample. During the in-person or remote visit, participants will register their sample with 23andMe, including ancestry and health information, and will authorize the research team to receive their results but will not automatically agree to other research through 23andMe. A member of the research team will assist participants in creating an online account through the 23andMe website. Participants can choose whether or not they want 23andMe to store their saliva sample. A member of the research team will show participants this option on the 23andMe website while helping them to register their sample. We will ask participants to log into their 23andMe account and give permission for the research team to download their genetic data and use it for research purposes. We will use these data to create a personalized genetic profile (RiskProfile) specific to participants' smoking-related genetic risk and likely responsiveness to medication. The data used for genomic profiles that we will create are part of the standard data generated by 23andMe. We will then randomize participants to one of two groups--Intervention (receive RiskProfile) or Control (receive brief cessation counseling and then receive RiskProfile at end of study)--and ask participants to return for a separate in-person or remote visit to receive their personalized genetic profile or brief cessation counseling and respond to the interview questions during that in-person or remote visit. The personalized genetic profile will be referred to as a genetics-informed "RiskProfile" and was refined through the developmental/design-oriented study with multiple stakeholder groups. Depending on the specific genetic profile of the participant, the RiskProfile will slightly differ; for example, for some, it will say "at very high risk", for some, it will say "at high risk", and for some, it will say "at risk". This will enable us to receive important feedback about the return of results procedure within the context of recently receiving personalized genetic results profile. These participants will then be asked to participate in a 30-day follow-up and then a 6-month follow-up, both comprising a 20-minute interview by phone or Zoom to examine changes in attitude and behavior as a result of receiving their personalized genetic results profile. Control group participants will receive their RiskProfile during the 6-month follow-up assessment. For the remote study, each participant's unique RiskProfile will be stored in the participant's unique folder on WUSTL Box platform and viewable to that participant and the research team only. Participants will also be asked to do a brief 10-15 minute phone follow-up approximately 18 months after their intervention to see if changes in attitude and behavior as a result of receiving their personalized genetic results profile have persisted.

Interviews will be audio recorded, and both audio and video recorded for Zoom interviews, for purposes of quality monitoring and assurance and to serve as a backup in case of technical difficulties (e.g., data entry software crash) during the interview that would risk data loss.

For the developmental activity to gather design-related feedback on the report card template, we will ask participants to review the report card and then share ideas on the clarity, simplicity, appeal, and usefulness of the sample report card, as well as how the design or formatting could be improved. Finally, we will ask a non-identifying question about whether the individual is a professional in the medical field and, if so, their general role in this field.

These campus-based interactions and interactions with NCADA staff (e.g., substance abuse counselors) will not be audio recorded.

Description of 23andMe and 23andMe Service: 23andMe, Inc. is a leading personal genetics company. Founded in 2006, the mission of the company is to help people access, understand and benefit from the human genome. The 23andMe® Service is a genetic service available directly to customers. The 23andMe Service includes personalized genetic reports that meet FDA standards for being scientifically and clinically valid and access to proprietary interactive tools to share, compare and discover with family and friends. The service is not intended to diagnose any disease. As noted in the 23andMe Privacy Statement ([www.23andme.com/about/privacy/](http://www.23andme.com/about/privacy/)), 23andMe employs software, hardware and physical security measures to protect the computers where customer data is stored, as well as robust authentication methods to access their systems. 23andMe customers' personal information and genetic data are stored in physically separate computing environments, which is in line with the industry standards for security.

AIM 2:

For Aim 2, we will engage current smokers (n=20) and clinicians and peer support specialists (n=10) in a partnering community health agency (Wellbridge) to adapt the RiskProfile for use in real-world community-based settings. Focus groups and participatory design activities will be used to guide the adaptation of the existing RiskProfile. We will conduct two focus groups with current smokers and counselors each to garner additional feedback on the RiskProfile intervention. Focus groups will attend to the feasibility and acceptability of the content and format of the version of the intervention in which participants engaged, including aspects of the intervention messaging that require clarification or that may lead to unintended consequences (e.g., negative behavioral or psychological reactions). All relevant intervention materials, including a sample RiskProfile, the standardized verbal script, and procedural manual, will be

reviewed by design participants for their relevance and fit within the community setting. Additionally, participants will be presented a de-identified recording of the RiskProfile being delivered to gather their feedback on the process. Finally, focus group participants will be presented an experimental version of the RiskProfile "PrecisionTx" for feedback. This version provides a hypothetical specific recommendation of medication based on genetic/metabolic factors. We will seek feedback on the concept of including specific recommendations of medication as part of the genetically-informed tool. The attached "GENIMP Aim 2\_Focus Group Guide" will be used as a guide for the focus groups.

Focus groups will be conducted using elements of design thinking (e.g., human-centered design) which emphasizes (1) developing empathy for target end-users (i.e., current smokers not yet ready to quit), (2) radical collaboration with input from a diverse set of perspectives, and (3) rapid prototyping by iteratively generating and vetting ideas of refinements to the tool in collaboration with participants (i.e., both current smokers and substance abuse counselors). Although the primary mode of delivery to be explored will be in-person sessions with substance abuse counselors, we will also explore the potential feasibility of more scalable intervention delivery platforms, including postal mail and web-based tools to deliver the intervention content. We will also examine perceptions of communication framing strategies among current smokers with relatively high and low genetic risks for smoking-related diseases.

A second group of current smokers (n=25) and counselors and peer support specialists (n=10) will be engaged in a small-scale feasibility trial of the genetic testing and intervention delivery protocol. Using the same study procedures in Aim 1 to guide participants to create a 23andMe account and provide their saliva sample via genetic testing, the second group of current smokers will undergo genetic testing while they are inpatient at Wellbridge and then be invited to receive their RiskProfile at the next counseling session via Zoom or in-person at Wellbridge, which will be delivered by a counselor or peer support specialist at Wellbridge, once their genetic data is ready.

Using structured assessments (attached for approval), we will assess the acceptability and feasibility of the RiskProfile using quantitative and qualitative metrics for both patients and clinicians. We will use modified versions of the Aim 1 assessments, the Acceptability of Intervention Measure (AIM), and the Feasibility of Intervention Measure (FIM). The AIM (4 items measuring approval, appeal, and favorability of the RiskProfile) and FIM (4 items measuring usability, intuitiveness, and comprehensibility) is measured on a 5- point scale (Completely disagree=1.0; Completely agree=5.0).

**1.14** Will participants be randomized?

Yes

**1.15** Will any of the following be used to collect information from the participant or others?

- Screening questions or screening/eligibility questionnaires
- Surveys
- Questionnaires
- Stimuli
- Any other written assessments

Yes

Attachment Name	Category	Version	Date Attached
Aim 2_V1 Assessment_07142023.docx	Subject Data Collection Instruments	1	07/14/23
Aim 2_Clinician V2 Assessment.docx	Subject Data Collection Instruments	1	07/14/23
Eligibility Screener for Focus Groups.docx	Subject Data Collection Instruments	1	10/07/22
V5 Assessment_7-10-23.docx	Subject Data Collection Instruments	4	07/11/23
V1 Assessments_08052021.docx	Subject Data Collection Instruments	15	08/05/21
Aim 2_V2 Assessment_071423.docx	Subject Data Collection Instruments	1	07/14/23
Open Ended Interview Questions_082620.docx	Subject Data Collection Instruments	7	08/28/20
Eligibility Script for GENIMP2_011421(1).docx	Subject Data Collection Instruments	4	01/14/21
V4 Assessments_7-10-2023.docx	Subject Data Collection Instruments	12	07/11/23
Locator Form.docx	Subject Data Collection Instruments	1	06/25/19
Script for Report Card Design Feedback_071919.docx	Subject Data Collection Instruments	5	07/22/19
GENIMP Aim 2_Focus Group Guide Final.docx	Subject Data Collection Instruments	1	10/07/22
V2 Assessments_7-10-23.docx	Subject Data Collection Instruments	17	07/11/23
V3 Assessments_7-10-23.docx	Subject Data Collection Instruments	17	07/11/23

**1.16** Does this project involve creating any audio, video, or photographs?

Yes

- 1.17** Does the study include any form of deception (e.g., providing participants with false information, misleading information, or withholding information about certain study procedures)?

Examples:

- Procedure includes a cover story that provides a plausible but inaccurate account of the purposes of the research.
- Participants will be provided with false information regarding the particular behaviors of interest in the research.
- Procedures include a confederate pretending to be another participant in the study.
- Participants will be told that the research includes completion of a particular task, when in fact, that task will not be administered.
- Study is designed to introduce a new procedure (or task) that participants are not initially told about.

No

- 1.18** Indicate any payments or reimbursements to participants (check all that apply)

- Cash
- Check
- Gift or Debit Card
- Forte Debit Card

- 1.19** Does this study have a plan to have an individual or committee review combined data from all participants on a periodic basis (such as summary or aggregate safety and/or efficacy data)?

No

- 1.20** What have you done to minimize any risks?

- No foreseeable risks

- 1.21** What are the potential benefits related to this project for:

- the participant (if any)
- benefits to society (if any)

Participants (adults who smoke) will have the direct benefit of receiving their individual genomic results profiles which could potentially improve their health behaviors (e.g., reduce tobacco use) and effectiveness of their treatment plans. Participants will receive genetic testing by 23andMe at no cost to them. From 23andMe they will receive genetic ancestry results and health results including carrier status reports, trait reports, and wellness reports.

The potential benefits to society are significant if the proposed research increases understanding of the best approaches to integrating genomic findings for substance use disorders into diverse settings. It is possible that the results of this study could be used to improve smoking and substance use disorder prevention and treatment strategies.

- 1.22** Provide a summary of the analysis methods you will use, including, if applicable, the data points or outcomes you will analyze.

For Aim 1, we will assess the acceptability of using genomic results (i.e., % agreeing to genetic testing, sharing results with others, recalling personal genomic results) and test whether smoking behaviors (frequency, heaviness) change more following delivery of the RiskProfile intervention than following brief cessation counseling. We expect higher rates of smoking cessation and reduction the Intervention group, particularly for those who accepted and recall their genomic results and whose health-related cognitions were altered (e.g., increased perceptions of disease risk, cessation benefits, value of cessation medications, self-efficacy). We will also examine whether the acceptability and recall of their genomic data for smoking cessation differ by age, sex, race, education level, or initial smoking behaviors. Given prior research on disparities in use of genomic results, we anticipate that acceptability and recall of results, or other mechanisms of behavior change, may be lower in African Americans, men, and heavier smokers. We will conduct multiple linear regression analyses to determine the extent to which race, initial smoking heaviness, or level of genetic risk predict acceptability and recall of genomic results, and whether receiving the RiskProfile predicts smoking cessation or reduction.

For Aim 2, we will identify key themes that will guide the adaption and improvement of the RiskProfile to deliver the tool in real-world settings. Adapting the RiskProfile will include data points consisting of refining the content, format, and delivery mode.

- 1.23** Provide the rationale or power analysis to support the number of participants proposed to complete this study.

Prior samples of a similar size and nature have allowed for adequate generalizability and power to detect relationships between variables of interest, including the ability to detect moderating relationships through interaction analyses. The current study is expected to mirror this prior experience, yielding adequate validity and range of responses. However, this study stands on its own as a pilot project, and any challenges related to power analysis do not negate the usefulness of this small-scale project to demonstrate proof of concept, establish the feasibility of returning genomic results to patients and physicians in a clinical setting, and provide the necessary rationale to test these implementation approaches with larger samples in future research.

- 1.25** Will any data from this project be stored for use in future research studies?

Yes - contribution for future use is optional

- 1.26** Does this project involve the collection or use of biological samples or genetic data?

Yes

**1.26.a** Will genetic/genomic research occur as part of this study?

Yes

**1.26.b** Do you plan to return any genetic/genomic results of testing generated as part of this study to participants (including either primary or incidental findings)?

Yes

**1.26.c** Attach a return of results plan.

Attachment Name	Category	Version	Date Attached
Return of Results Plan_082620.docx	Return of Results Plan	7	08/28/20

**1.26.d** Will biologic samples or genetic data be stored for future research?

No

**1.26.f** Will participants be able to request at a later time that the biological samples or genetic data be destroyed?

No

**1.27** Are you requesting institutional certification to contribute human data or samples to a repository or database for broad sharing (public or restricted access)?

No

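### Aim 1 participants are randomized before being asked back for the delivery visit, so some may be randomized and never receive either session

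*Combined protocol and SAP*

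**What the plan says.** The instruction for item 1.13 is "Provide a detailed description in sequential order of the study procedures following the consent process", so the order of the sentences can be read as the order of events. For Aim 1 that order is:

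1. Baseline interview, offer of genetic testing, saliva sample, and release of the genetic data to the team.
2. Profile made: "We will use these data to create a personalized genetic profile (RiskProfile) specific to participants' smoking-related genetic risk".
3. Allocation: "We will then randomize participants to one of two groups".
4. Then the team is to "ask participants to return for a separate in-person or remote visit to receive their personalized genetic profile or brief cessation counseling".
5. Follow-up: "These participants will then be asked to participate in a 30-day follow-up and then a 6-month follow-up".
6. Deferred delivery: "Control group participants will receive their RiskProfile during the 6-month follow-up assessment".

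Item 1.22 says the analysis will test whether smoking behaviors "change more following delivery of the RiskProfile intervention than following brief cessation counseling". It names no analysis population and gives no rule for people who were randomized but did not return. Item 1.12 says that for Aim 1 "participants will include approximately 250 adults who are current smokers"; the number in the randomized pilot is not given separately. Item 1.23 states no significance level, power, effect size, allocation ratio or allowance for non-attendance.

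**The concern.** Allocation comes before a further decision by the participant, namely whether to attend the delivery visit. Nothing in the protocol ties allocation to attendance, describes concealment up to the visit, or provides for an arm-neutral invitation. It is also unclear whether the follow-up sentence in item 1.13 covers people who were randomized but never came, because it follows the account of the delivery visit and refers back to participants already mentioned.

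Two things are at stake.

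- **Selection.** If participants know their arm when they decide whether to attend, attendance may depend on the arm and on motivation to quit. Comparing only attenders would then compare groups that randomization no longer balances.
- **Dilution.** Analysing everyone as randomized protects against that selection, but the estimated effect is averaged over people who received nothing.

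The protocol gives no reason for allocating early. The profile is made before allocation, controls need one too, and both arms use the same kind of visit.

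**Working it through.** The plan has no sample-size, power or attendance figure to reproduce. What follows is an illustration of dilution only.

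**Inputs**

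- From the protocol: about 250 Aim 1 participants (item 1.12), used here as the number reaching this step.
- Assumed: 1:1 allocation (125 per arm), two-sided alpha 0.05, 80% power at full attendance, and a share q in each arm that never attends. Non-attenders show no difference between arms, and everyone randomized is followed up. The range tried is q = 5% to 30%.

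**Step 1. Relative information (full attendance = 1)**

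- Randomize before the visit: the sample stays whole but the effect shrinks to (1 − q), so information is (1 − q)².
- Randomize at the visit: the effect is whole but the sample shrinks to (1 − q), so information is (1 − q).

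At q = 15%:

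- current order: 0.85² = 0.7225
- after the change: 0.85
- ratio: 0.7225 / 0.85 = 0.85, an avoidable loss of about 15%
- equivalent sample: 1 / 0.85 = 1.18 times as many people for the same precision relative to the effect

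**Step 2. Power**

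The standardized effect that gives 80% power with 125 per arm is (1.960 + 0.842) × √(2/125) = 0.354. Power is then Φ(effect × √(n/2) − 1.960), with:

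- before the visit: n = 125 and effect 0.354 × (1 − q)
- at the visit: n = 125 × (1 − q) and effect 0.354

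| q | Randomized without a session, of 250 | Power, current order | Power, at visit | Sample inflation, current order | Sample inflation, at visit |
|---|---|---|---|---|---|
| 5% | 12.5 | 75.9% | 78.0% | 1.11 | 1.05 |
| 10% | 25 | 71.3% | 75.7% | 1.23 | 1.11 |
| 20% | 50 | 61.1% | 70.7% | 1.56 | 1.25 |
| 30% | 75 | 50.0% | 65.0% | 2.04 | 1.43 |

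The gap is about 2, 4, 10 and 15 percentage points.

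**Step 3. Check on a binary outcome**

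The control rate is set to 21%, borrowed from the baseline quit-attempt figure in item 1.5 purely as an illustration. The intervention rate that gives 80% power at full attendance is then 37%. At q = 10% power is 71.8% versus 75.7%, and at q = 20% it is 62.3% versus 70.6%. The pattern is the same.

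**What this leaves out.** Loss that differs between arms is not quantified, because the documents give no basis for a figure.

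**The case against.** **The exposed interval may be short.** Randomization already follows testing and profile creation, so losses during the laboratory wait fall before allocation. Only the step from allocation to visit is exposed. The protocol gives neither its length nor the number lost, and allocation could be close to the visit. This stands, and it limits the likely size.

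**Bias depends on the analysis.** If everyone randomized is followed and analysed by arm, arm-dependent attendance does not bias the comparison. This also stands. But the protocol specifies neither that analysis nor follow-up of non-attenders, and dilution would remain.

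**Early allocation has some value.** It shows uptake of each offer by arm and keeps the result applicable to everyone offered a session, which suits a pilot with feasibility aims. This has limited force: attendance at the delivery visit is not among the acceptability measures listed in item 1.22, and overall attendance could still be reported.

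**A reader might infer that the invitation tells controls they will wait 6 months for their profile, so that they stay away.** The text does not support this as fact. The sentence in item 1.13 describes both arms at once and fits a single neutral invitation equally well. The participant correspondence and the Return of Results Plan are attachments that are not part of these documents. Item 1.21 adds that participants receive ancestry and health results from 23andMe, so controls are not left without any genetic results. Disclosure is possible, not established.

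**The change may come late.** Materials for the 18-month contact are dated April to August 2023 (attachments under items 1.8 and 1.15), which suggests that some delivery visits had already taken place. Reordering would help only people not yet randomized.

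**Conclusion.** The point holds as a correctable weakness in design. The protocol's sequence allows people to be randomized and never given either session, and nothing later in the plan deals with them. Selection bias arises only if attendance differs by arm and attenders alone are compared. Dilution arises under an as-randomized analysis whenever anyone fails to attend.

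On the assumed 15% non-attendance in each arm, the loss that a change of order would avoid is about 15% of the information. On the assumed 250 people, power would be about 71% versus 76% at 10% non-attendance, and 61% versus 71% at 20%. All of these rest on attendance rates that the documents do not give.

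Two stronger readings should be resisted. A reader might take the loss at 15% non-attendance to be 28% (1 − 0.7225). That compares the current order with perfect attendance, which randomizing at the visit would not deliver either. A reader might also conclude that the change is free. The protocol supports no extra visits, tests or profile preparation, but it is silent on staffing, and the change narrows the population to which the result applies.

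**What to change.** In item 1.13, randomize at the start of the delivery visit, once attendance is confirmed and before either session is delivered. Conceal allocation until that moment; REDCap is already in use for the study, and its randomization module is one way to do this. Send one arm-neutral invitation to everyone. Report people who do not attend as losses before randomization.

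For anyone already randomized under the current order, state in item 1.22 that they are analysed as randomized. Seek 30-day and 6-month data from those who did not attend, and report by arm the number never given a session.

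**Cost.** Two existing steps change places, with no added visit or test. Slightly fewer people are randomized, the result applies to people who attend the visit, uptake of each offer by arm is no longer observed, and staff must be ready to give either session.
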